9.1.4. Subject Death

Death is not an AE but instead an outcome of an AE. In rare cases the known cause of death or one AE may not be able to be declared as the major contributor to death, however when possible death should be reported as an outcome.

Any ongoing or unresolved AEs at the time of death will be indicated as "ongoing" on the CRF.

Attempts will be made by the Investigative site to obtain death certificates, autopsy reports, and device explants when at all possible.

CONFIDENTIAL INFORMATION

MD133246 Protocol Template

Revision#: 1

Doc Type: GC

9.2. Clinical Events Committee

An independent Clinical Event Committee(CEC) will be established to review all safety-related and clinical events during the study. The committee will be composed of three members representing Interventional Radiology, Interventional Cardiology and/or Vascular Surgery.

The scope of the CEC is as follows:

1. General review and adjudication of Adverse Events to include:
 - a. Agreement on the Serious Adverse Event designation as coded by Site
 - b. Agreement of the relationship of the AE to the study device, index procedure, or disease
 - c. Review of MedDRA coding for consistency between similar events
2. Death summary review and agreement of relationship of the death to the study device or index procedure as reported by the Site
3. Protocol Deviation review (as appropriate)
4. General study consultation (as appropriate)

The CEC meetings will be scheduled approximately 3 times per year depending on the rate of enrollment. At minimum, safety data will be reviewed by the committee prior to each 6-month and/or annual due date for a FDA interim report.

10. Statistical Analysis

10.1. Primary Endpoint Analysis

10.1.1. Primary Effectiveness

The primary effectiveness endpoint is Primary Patency at 12 months post-procedure. Primary patency will be estimated through 365 days along with a 95% confidence interval using Kaplan-Meier analysis. Equivalent analysis will be performed with regards to the primary patency partitioning the data by lesion length (< 230 mm and \geq 230mm). All results will be compared to that obtained in the RELINE study.

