3.2.3. Secondary Endpoints

The secondary endpoints for this study include:

- Acute Procedural Success
- Primary Patency at 30 days, 12, 24 and 36 months
- Primary Assisted at 30 days, 12, 24 and 36 months
- Secondary Patency at 30 days, 12, 24 and 36 months
- Freedom from Target Lesion Revascularization at 30 days, 12, 24 and 36 months
- Freedom from Major Amputation at 30 days, 12, 24 and 36 months
- Change in Ankle-Brachial Index from pre-procedure at 30 days, 12, 24 and 36 months
- Change in Rutherford Category from pre-procedure at 30 days, 12, 24 and 36 months
- Stent Fracture Assessment at 12, 24 and 36 months

4. Study Population

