10.2.2. Primary Patency

Primary patency is defined as patent blood flow through the study device, which requires either a PSVR measurement ≤ 2.5 or patent flow indicated by the Core Lab, without repeat intervention. Primary patency will be estimated at 30 days, 12, 24 and 36 months along with a 95% confidence interval using Kaplan-Meier analysis.

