2.4 Primary Endpoints

2.4.1 Primary Patency at 12 months Post-procedure

The primary effectiveness endpoint is Primary Patency at 12 months post-procedure. This will be estimated through 365 days along with a 95% confidence interval using Kaplan-Meier analysis. Equivalent analysis will be performed with regards to the primary patency partitioning the data by lesion length (< 230 mm and ≥ 230 mm). All results will be compared to that obtained in the RELINE study.

CONFIDENTIAL INFORMATION

MD133254 Statistical Analysis Plan Template
Revision#: 1
Doc Type: GC

2.4.2 Procedure or Device-related Serious Adverse Events Within 30 days of the Index Procedure

The primary safety endpoint is procedure- or device-related Serious Adverse Events within 30 days of the index procedure. The total number of events as well as the number of Subjects experiencing them will be tabulated along with a 95% confidence interval.

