2.5.2 Primary Patency

Primary patency is defined as patent blood flow through the study device, which requires either a PSVR measurement ≤ 2.5 or patent flow indicated by the Core Lab, without repeat intervention. Primary patency will be estimated at 30 days, 12, 24, and 36 months along with a 95% confidence interval using Kaplan-Meier analysis.

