5.4 Primary Endpoints

5.4.1 Primary Effectiveness - Primary Patency at 12 Months Post-procedure

Both the ITT and PP populations will be used with the following decision rules for calculating the primary patency at 12 Months post-procedure.

CONFIDENTIAL INFORMATION

MD133254 Statistical Analysis Plan Template
Revision#: 1
Doc Type: GC

5.4.2 Primary Safety - Procedure or Device-related Serious Adverse Events Within 30 Days of the Index Procedure

Both the ITT and PP populations will be used with the following decision rules for calculating the serious adverse events within 30 days of the index procedure.

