5.5.2 Primary Patency

Both the ITT and PP populations will be used with the following decision rules for calculating the primary patency through Kaplan-Meier time to event analysis.

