5.5.5 Freedom from Target Lesion(s) Revascularization (TLR)

Both the ITT and PP populations will be used with the following decision rules for calculating the secondary patency through Kaplan-Meier time to event analysis.

CONFIDENTIAL INFORMATION

MD133254 Statistical Analysis Plan Template
Revision#: 1
Doc Type: GC

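### Does listing 12-month primary patency as both a primary and a secondary endpoint leave two possible values for it?

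*Protocol*

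**What the plan says.** Protocol 10.1.1 makes primary patency at 12 months the primary effectiveness endpoint and says: "Primary patency will be estimated through 365 days along with a 95% confidence interval using Kaplan-Meier analysis". SAP 2.4.1 agrees: "This will be estimated through 365 days along with a 95% confidence interval using Kaplan-Meier analysis".

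Protocol 3.2.3 lists among the secondary endpoints "Primary Patency at 30 days, 12, 24 and 36 months". Protocol 10.2.2 gives the method, "Primary patency will be estimated at 30 days, 12, 24 and 36 months along with a 95% confidence interval using Kaplan-Meier analysis", and SAP 2.5.2 repeats it: "Primary patency will be estimated at 30 days, 12, 24, and 36 months along with a 95% confidence interval using Kaplan-Meier analysis".

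The SAP then introduces rules twice. Section 5.4.1 announces "the following decision rules for calculating the primary patency at 12 Months post-procedure", and section 5.5.2 announces "the following decision rules for calculating the primary patency through Kaplan-Meier time to event analysis". Neither list appears in the public copy.

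Protocol Table 4 allows 45 days either side of day 365 for the 12-month visit. Scheduled duplex scans are at 30 days and at 12, 24 and 36 months only (Protocol 5.1 and 5.7).

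**The concern.** One quantity has two labels and two announced rule lists, and no visible sentence says that both give the same number. The secondary text also gives no day number for 12 months, whereas the primary text gives day 365.

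The rules could matter. Primary patency is judged by scan or by repeat intervention. A failure that causes no symptoms after the 30-day visit would usually be found first at the 12-month scan, and that scan may be done after day 365. If such failures carry the scan date, some fall outside the day-365 estimate. If patent subjects are censored at their scan, those scanned early leave the risk set before day 365. Should the two lists differ on these points, a report could carry two 12-month figures, and the one compared with RELINE would depend on which list was used.

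There is also a sign of copied text: SAP 5.5.5, on target lesion revascularization, announces "the following decision rules for calculating the secondary patency through Kaplan-Meier time to event analysis", and 5.5.6, on major amputation, has the same line. That invites a check on which list governs which endpoint.

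**Working it through.** The documents give no patency rate, and the sample size section is withheld, so there is no stated figure to reproduce.

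**1. Do the primary and secondary descriptions differ?**

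| Element | Primary (Protocol 10.1.1, SAP 2.4.1) | Secondary (Protocol 10.2.2, SAP 2.5.2) |
|---|---|---|
| Definition | Protocol 3.2.1, SAP 2.3 | the same |
| Method | Kaplan-Meier, 95% CI | Kaplan-Meier, 95% CI |
| Populations | ITT and PP (Protocol 10.6.2, SAP 5.2) | ITT and PP |
| Time | day 365 | 12 months, which Table 4 centres on day 365 |

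No element conflicts. Read together, these describe one curve evaluated at 30 days and at 12, 24 and 36 months.

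**2. Counts from the documents.**
- Window: 365 − 45 = 320 to 365 + 45 = 410, which is 91 days. Days 366 to 410 number 45, and 45/91 = 49.5%. This is a share of permitted days, not of expected scans.
- One silent failure counted or not by day 365, with no earlier censoring: 1/108 = 0.9 points overall, and 1/20 = 5.0 points in a long-lesion group at its minimum of 20.
- For scale, the 95% CI half-width at an assumed 75% patency is 1.96 × √(0.75 × 0.25/108) = 8.2 points.

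**3. Size if the withheld rules use the scan date.** Assumptions: n = 108; 12.5% clinical failures spread evenly over days 31 to 365; 5, 12.5 or 20% silent failures seen at the 12-month scan; four visit patterns, with the normal ones truncated to days 320 to 410. The shift is measured against counting every 12-month-visit failure by day 365.

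If patent subjects stay at risk, shift = silent share × share of scans after day 365. For uniform visits this is 0.05 × 0.495 = 2.5 points up to 0.20 × 0.495 = 9.9 points. The last column comes from simulation.

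| Visit pattern | Share after day 365 | Kept at risk (5/12.5/20%) | All patent subjects censored at scan (5/12.5/20%) |
|---|---|---|---|
| Uniform | 0.495 | +2.5/+6.2/+9.9 | +1.0/+3.7/+6.7 |
| Normal(378, 20) | 0.721 | +3.6/+9.0/+14.4 | +3.2/+8.4/+13.6 |
| Normal(352, 20) | 0.262 | +1.3/+3.3/+5.2 | −2.3/−3.3/−3.4 |
| Normal(350, 15) | 0.154 | +0.8/+1.9/+3.1 | −5.0/−8.6/−10.7 |

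**4. Does the negative half apply?** It requires that no patent subject is seen after the 12-month scan. Protocol 10.6.1 and SAP 5.1 place the formal analysis after every subject has completed 36 months or withdrawn. A subject who is patent at day 340 and returns at 24 months is at risk on day 365. Under normal(350, 15), the simulated shift by assumed share of patent subjects with a later visit is:
- none: −5.1/−8.7/−10.6
- 50%: about −0.7/−1.0/−0.9
- 90%: +0.5/+1.5/+2.4

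Even the 1-year report is not a cut with no later visits. With even accrual over 730 days, the last 12-month window closes on day 730 + 410 = 1140. Subjects enrolled by day 1140 − 775 = 365, which is half of them, have by then passed the end of their 24-month window (730 + 45 = 775).

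**The case for a change.** The strongest case for acting is that clarification is cheap and the effect could be material. Under scan-date rules, a shift of up to 9.9 points with uniform visits exceeds the 8.2-point half-width, and the estimate is to be compared with RELINE. One line could say that the secondary 12-month figure is the primary estimate. At 36 months the protection from later visits disappears: the visit itself ends participation (Protocol 5.10), so a patent scan on days 1050 to 1094 is followed by no scheduled scan that would carry the subject to day 1095. The copied lead-ins under SAP 5.5.5 and 5.5.6 show that the wording was not checked line by line.

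Most of these facts stand. The window does straddle the reading day, the convention would matter if it were the scan date, and the day-1095 reading depends on it most. They do not show a fault. Event dates and censoring dates are what decision rules for a Kaplan-Meier endpoint normally contain, and the plan announces such rules for each endpoint. Asking what they say is asking to see withheld text. The additional analyses are withheld too, so a sensitivity analysis may already exist. The one-line statement would alter no number, because the visible specifications already match. The lead-ins under 5.5.5 and 5.5.6 are a clerical slip: the section titles make the intended endpoints clear, and the slip says nothing about 5.4.1.

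**Conclusion.** The concern does not call for a change. Listing 12-month patency under both headings is a redundancy. The two descriptions share definition, method, confidence level, populations and target day, and an analyst would read both from the same curve. Two lead-ins reflect a SAP that gives each endpoint its own subsection; nothing visible shows that the lists differ.

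The sensitivity to dating is real but conditional. If silent failures are dated at the scan and patent subjects have later follow-up, the day-365 figure at the formal analysis would shift mostly upward: about +2.5 to +10 points with uniform visits, +0.5 to +5 with early visits and +3.6 to +14 with late visits. These figures rest on assumed silent-failure rates of 5 to 20%, assumed visit patterns and an assumed dating rule, none of which is in the documents. The shifts down to about −11 points belong to a data cut in which patent subjects have no later visit. No hypothesis test or performance goal is visible that such a shift could overturn.

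This judgement covers the visible text only. It does not establish that the withheld rules are sound, at day 365 or at day 1095.

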10.1.2. Primary Safety

The primary safety endpoint is procedure or device-related Serious Adverse Events within 30 days of the index procedure. The total number of events as well as the number of Subjects experiencing them will be tabulated along with a 95% confidence interval.

10.2. Secondary Endpoint Analysis

10.2.1. Acute Procedural Success

Acute Procedural Success is defined as successful delivery of the study device and complete coverage of the target lesion without a procedure or device-related Serious Adverse Event prior to hospital discharge. This will be tabulated omitting all Subjects with unknown status.

CONFIDENTIAL INFORMATION

MD133246 Protocol Template

Revision#: 1

Doc Type: GC

10.2.2. Primary Patency

Primary patency is defined as patent blood flow through the study device, which requires either a PSVR measurement ≤ 2.5 or patent flow indicated by the Core Lab, without repeat intervention. Primary patency will be estimated at 30 days, 12, 24 and 36 months along with a 95% confidence interval using Kaplan-Meier analysis.

10.2.3. Primary Assisted Patency

Primary assisted patency is defined as blood flow through the study device regardless of repeat interventions to maintain patency prior to occlusion. Blood flow will require confirmation by the study core lab. Primary assisted patency will be estimated at 30 days, 12, 24 and 36 months along with a 95% confidence interval using Kaplan-Meier analysis.

10.2.4. Secondary Patency

Secondary patency is defined as blood flow through the study device regardless of repeat interventions to restore patency after occlusion. Blood flow will require confirmation by the study core lab. Secondary patency will be estimated at 30 days, 12, 24 and 36 months along with a 95% confidence interval using Kaplan-Meier analysis.

10.2.5. Freedom from Target Lesion Revascularization (TLR)

Target Lesion Revascularization is defined as a repeat intervention within the study device and 5 mm proximal or distal to the edge of the study device to maintain or re-establish patency. Freedom from TLR will be estimated at 30 days, 12, 24 and 36 months along with a 95% confidence interval using Kaplan-Meier analysis.

10.2.6. Freedom from Major Amputation

Major Amputation is defined as removal of the study limb above the metatarsals, resulting from a vascular event. Freedom from major amputation will be estimated at 30 days, 12, 24 and 36 months along with a 95% confidence interval using Kaplan-Meier analysis.

10.2.7. Change in Ankle-Brachial Index (ABI)

Ankle Brachial Index is defined as the ankle systolic pressure in the study limb divided by the highest brachial systolic pressure in either arm. The minimum, maximum, median, mean and standard error will be reported for the change in ABI relative to that measured pre-procedure at 30 days, 12, 24 and 36 months. All values measured within the defined window will be used in calculation.

10.2.8. Change in Rutherford Category

The change in Rutherford Category, measured relative to that obtained pre-procedure, will be assessed at 30 days, 12, 24 and 36 months. The minimum, maximum, median, mean and standard error will be reported as well as the counts for each outcome. All values measured within the defined window will be used in calculation.

CONFIDENTIAL INFORMATION

MD133246 Protocol Template

Revision#: 1

Doc Type: GC

10.2.9. Stent Fracture

Device stent fractures will be assessed by the study core lab through x-ray images. A table of all stent fractures, which are clearly distinguishable from previously implanted stents, will be reported at 12, 24 and 36 months. All values measured within the defined window will be used in tabulation.

10.3. Additional Analysis

[REDACTED]

10.4. Sample Size

[REDACTED]

10.5. Blinding Scheme

Due to the fact that there is only one study treatment, neither the Subjects nor Investigators will be blinded to the study treatment.

10.6. Data Analysis

10.6.1. Timing of Analyses

Reports will be prepared when follow-up is complete for endpoints of the study (e.g. 1-year, 2-year, and 3-year). Additional interim analyses and reports will be done in order to comply with regulatory reporting requirements. This will consist of, at a minimum, the physical characteristics of enrolled Subjects as well as tabulations of all interventions and adverse events. In addition, listings of all interventions and adverse events will be prepared. Once all Subjects have either completed 36 months of follow-up or been withdrawn from the study, a formal statistical analysis will be performed to evaluate all study endpoints.

10.6.2. Analysis Populations

Both of the following populations will be used for analyses of primary and secondary endpoints.

- (1) Intent to treat – All patients assigned to the study treatment, regardless of whether or not they received it or have any protocol violations.
- (2) Per protocol – A subset of the ITT population consisting of Subjects receiving the study device which meet all inclusion and exclusion criteria and without any major protocol violations.

10.6.3. Pooling of Data

Data from all study sites will be pooled on a clinical basis, i.e., the study sites will follow a common protocol, the study will be monitored to assure compliance with the protocol and applicable government regulations, and the data collection and handling procedures will be the same at all study sites.

CONFIDENTIAL INFORMATION

MD133246 Protocol Template

Revision#: 1

Doc Type: GC

11. Ethical and Regulatory Considerations

11.1. Statement of Compliance

The study will be conducted in compliance with this protocol, International Conference on Harmonization Good Clinical Practice E6 (ICH-GCP), and applicable regulatory requirements.

The following are applicable to this study:

21 CFR Part 11	Electronic Records; Electronic Signatures
21 CFR Part 50	Protection of Human Subjects
21 CFR Part 56	Institutional Review Boards
ICH-GCP E6	International Conference on Harmonisation Regulations Guideline For Good Clinical Practice

11.2. Compliance Responsibilities

The Sponsor will conduct the study in accordance with all applicable regulations and laws. The Sponsor will be responsible for documenting that Investigators have the necessary skills, training and information to properly conduct the study. The Sponsor will ensure proper monitoring of the study and ensure the Site has obtained IRB/EC approval prior to enrollment. The Sponsor will provide information to the Investigators, the reviewing IRB/EC and the Food and Drug Administration concerning the progress of and any new material information about the study.

The Investigator will conduct the study in accordance with all applicable regulations and laws, any relevant agreements, the study protocol, and all approval conditions of the reviewing IRB/EC and the Food and Drug Administration. The Investigator will ensure IRB/EC approval is obtained prior to enrollment, maintained throughout the course of the study, and that all IRB/EC reporting requirements are met. The Investigator is responsible for protecting the rights, safety, and welfare of Subjects under the Investigator's care and for the control of devices under investigation. The Investigator is also responsible for ensuring that informed consent is properly obtained.

11.3. Informed Consent

The Investigator shall ensure that all potential Subjects for this study are provided with a consent form describing this study and sufficient information to make an informed decision about their participation.

CONFIDENTIAL INFORMATION

MD133246 Protocol Template

Revision#: 1

Doc Type: GC

The formal consent of a Subject, using the IRB/EC-approved consent form, must be obtained by the Investigator before that Subject undergoes any study-related procedure. The consent form will be signed and personally dated by the Subject and the person who conducted the informed consent discussion. The original signed informed consent form will be retained in the Subject records. A copy of the informed consent document will be given to the Subject for his or her records. Any significant, new information which emerges while the study is in progress that may influence a Subject's willingness to continue to take part in the study will be provided to the Subject.

The Investigator shall ensure that documentation of the acquisition of informed consent is recorded in each Subject's records in accordance with applicable regulations.

11.4. Independent Ethical Review

The Investigator shall not enroll any Subjects prior to obtaining approval for the study from a properly constituted independent IRB/EC.

The Investigator will submit the protocol, informed consent forms, and other information to be provided to Subjects such as survey instruments or questionnaires, and any proposed advertising/recruitment materials, to the IRB/EC for written approval.

11.5. Conflict of Interest

All Investigators will follow applicable laws and regulations as well as the conflict of interest policies of their Site and the reviewing IRB/EC.

11.6. Confidentiality

All Subject records will be kept confidential to the extent provided by applicable laws and regulations. The study monitors and other authorized representatives of the Sponsor may inspect all documents and records required to be maintained by the Investigator, including but not limited to medical records.

Such records may also be reviewed by the Site's IRB/EC and other regulatory bodies (e.g., FDA).

The Investigator will inform the Subjects that their records will be reviewed.

6 ANALYSIS SPECIFICATIONS	11
6.1 SAS ANALYSIS DATASET SPECIFICATIONS	11
6.2 PRIMARY ENDPOINT	11
6.3 VERIFICATION LEVEL FOR STATISTICAL OUTPUT	11
7 DATA SETS, TABLES, FIGURES, AND LISTINGS	11
7.1 ANALYSIS TABLES	12
7.2 ANALYSIS LISTINGS	13
7.3 ANALYSIS FIGURES	13
8 REFERENCES	13
8.1 MD111325	13
8.2 MD119211	13

CONFIDENTIAL INFORMATION

MD133254 Statistical Analysis Plan Template
 Revision#: 1
 Doc Type: GC

1 Introduction

This Statistical Analysis Plan (SAP) describes the statistical analyses planned to address the objectives of ISR 14-04 clinical study. This SAP summarizes the analyses that will be performed to determine the safety and effectiveness of the GORE® VIABAHN® Endoprosthesis for the treatment of in-stent restenosis in the superficial femoral artery. This SAP outlines tables, figures, and listings that are included in reports for the ISR 14-04 clinical study.

2 Study Design

